#### ***ii) Secondary Analysis***

Short-term (intra-operative and early post-operative) and long-term postoperative complications will be documented and collected prospectively at each site by the study coordinator. Group comparisons will be performed using the Pearson's chi-square test or binomial test, where appropriate for these categorical variables. Repeated measure analysis will be used for Breast Aesthetic Score at 6 and 12 months post mastectomy. The Modified Baker Scale for capsular contracture results in an ordinal variable which will be compared using the Pearson's chi-square test.

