#### Preliminary cost-effectiveness analysis

The average piece of AlloDerm (LifeCell Corp, Branchburg, N.J.) for one-stage implant reconstruction is thick and 6cm X12cm in dimensions, and costs \$2105 in Canadian currency. Preliminary comparison of the two surgical techniques was performed by retrospectively reviewing all case costing data for 10 randomly selected study subjects who underwent either one-stage AlloDerm or two-stage TE/I reconstructions as part of the RCT from November 2009 to September 2010 through the University Health Network Accounting Department. Our hospital's Accounting Department collects cost data for every ambulatory clinic visit, emergency department visit, surgery, and in-hospital stay. We found that there were on average 5 more clinic visits (TE inflation sessions) in the two-stage TE/I than one-stage AlloDerm group. The average direct cost to the hospital was \$1,572 and \$595.91 more expensive per patient for the two-stage TE/I than AlloDerm assisted one-stage method for unilateral and bilateral reconstructions respectively. (APPENDIX 1)

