#### Interim analysis of complication rates

An interim analysis of short-term complications revealed similar rates of postoperative complications between the two arms of the trial. In the one-stage AlloDerm assisted implant study arm, the rate of major complications is 0 and the rate of minor complications is 7%. There has been 1 case of cellulitis and 1 case of infected seroma both successfully treated with antibiotics. In the two-stage TE/I control arm, the rate of major complications is 4% and the rate of minor complications is 12.5%. In this arm, there were 2 cases of cellulitis successfully treated with antibiotics, 1 case of incisional dehiscence managed with conservative dressing changes, and 1 case of infected seroma that resulted in premature removal of the expander.

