#### **iib-6. Postoperative treatment**

In **Group B**, at 2 weeks after the operation, office expansion will be undertaken and continued on a biweekly basis. With each expansion, the endpoint of expansion will include either: (1) persistent blanching or congestion of the mastectomy flap; or, (2) patient discomfort. The expansion phase will be considered complete once the volume in the expanded breast represents 100 percent (+/- 20 percent) of the recommended expander volume. If required, postoperative chemotherapy is generally given during the expansion period. Expanders are then exchanged approximately between 4-6 weeks following the completion of chemotherapy or 3-6 months following completion of inflation. All patients in group B will undergo a second exchange procedure at which time the expander is removed and a permanent implant is placed. In all instances, the permanent implant to be used will be anatomic cohesive silicone gel implants (Style 410, Allergan, Santa Barbara, CA).

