## **iib-8. Outcomes and their measurements**

### **Primary Outcome: *Patient-Reported Satisfaction and Quality of Life***

Patient satisfaction and quality of life will be measured using the Breast Q $\circ$  as a self-administered questionnaire. The Breast Q $\circ$  has 2 subscales that examine the two different domains: satisfaction and psychosocial function. The scores generated for each subscale will be transformed on a scale from 0-100, lowest to highest summary scores respectively. Scale validity and reliability are supported by the high Cronbach's alpha coefficient (>0.80) and intra-class correlation coefficients (>0.70). The scores generated for each subscale will be transformed on a scale from 0-100, lowest to highest summary scores respectively. Participants will be asked to complete the pre-operative module of the Breast Q $\circ$  questionnaire at 2 weeks prior to the mastectomy.(APPENDIX 4) Post-operatively, they will be requested to complete the post-operative module of the Breast Q $\circ$  at 2 weeks following immediate reconstruction, as well as 6 months and 1 year following the completion of the reconstruction. (APPENDIX 5) The questionnaires will be self-administered and mailed to the participants with return envelopes and prepaid postage. To compensate our study patients for their participation, a monetary reimbursement (\$10) will be available upon completion. The Dillman method will be used to encourage patient response.

The **secondary outcomes** will include a comparison of:

1. **short and long-term complication rates**: Short-term complications are intra- and post-operative complications occurring within two months of surgery and long-term complications occur later than two-months. They will be documented and collected prospectively.

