2. **long-term aesthetic result**: Evaluation of the overall aesthetic result and capsular contracture grade will be performed at six months and one year following the completion of reconstruction. A routine physical examination will be performed by the attending surgeon and photographic documentation (5 standardized photographs) of the reconstruction will be obtained at the six month and one-year follow-up visit. A panel of three independent, blinded observers will subsequently evaluate the overall aesthetic result using the three-point, five item, Breast Aesthetic Score described by Lowery with the use of photographic documentation. Capsular contracture will be graded by the examining physician and will be graded using the Modified Baker Scale for Reconstructed Breasts, which is widely accepted to be the gold-standard measure of capsular contracture grade.
3. **cost-effectiveness**: Costs and effects will be simultaneously analyzed by collecting person-level cost and effect data. The cost data will come from hospital cost accounting systems and patient reports. The patient outcome data will be collected at months 6 and 12 months post-mastectomy by Breast Q $\circ$

and EQ-5D. The frequently used generic HRQoL instrument EQ-5D will be piggy-backed to the Breast QoL at the 2 post-mastectomy time-points to generate a utility value for current health. The primary measure of effectiveness will be the Breast Q score and the secondary measure will be quality adjusted life years (QALY) as measured by the EQ-5D (APPENDIX 6)

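### Short-term complications have no assessment times common to both arms, and only the two-stage arm has scheduled visits in that window, so minor events may be found more often in the control arm

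*Combined protocol and SAP*

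**What the plan says.** Section 9c ii (Secondary Analysis) states that short- and long-term complications "will be documented and collected prospectively at each site by the study coordinator" and compares them with a Pearson chi-square or binomial test. Section iib-8 (Outcomes and their measurements) defines the periods: "Short-term complications are intra- and post-operative complications occurring within two months of surgery and long-term complications occur later than two-months". Neither section gives assessment times, a checklist, definitions of minor and major, or masked adjudication. Masked observers appear only for the aesthetic photographs.

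Section iib-6 (Postoperative treatment) sets visits for the two-stage arm alone: "at 2 weeks after the operation, office expansion will be undertaken and continued on a biweekly basis". It adds that "All patients in group B will undergo a second exchange procedure". It gives no visits for the one-stage arm.

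The examination that the plan fixes for both arms is in iib-8, under the aesthetic outcome: "A routine physical examination will be performed by the attending surgeon" at six months and one year after reconstruction is complete.

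Section iia-3 (Preliminary Data) reports from a cost review of 10 subjects that "there were on average 5 more clinic visits (TE inflation sessions) in the two-stage TE/I than one-stage AlloDerm group". The hypothesis in Specific Aims is that ADM does not raise short- or long-term complications. No margin is given.

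**The concern.** Expansion visits start inside the two-month window. At each one a clinician sees the breast, and a mild cellulitis, a seroma or a small wound separation can be noted and passed to the coordinator. A one-stage patient has no scheduled equivalent, so a mild event could settle, or be treated elsewhere, without reaching the trial record.

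If that happens, the comparison measures opportunity to detect as well as occurrence. The expected direction is fewer recorded minor events in the ADM arm. Because the hypothesis is one of no increase, under-recording in that arm moves the result towards the conclusion the investigators expect, and an unadjusted test cannot reveal it. What is at stake is the short-term minor part of one secondary outcome, which is nevertheless part of the safety comparison for a technique that the protocol calls novel.

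**Working it through.** **1. The interim rates reproduce.** Randomized numbers (iia-3): one-stage 17 + 10 = 27; two-stage 16 + 8 = 24. Event counts come from the interim analysis of complication rates.
- One-stage minor: 1 cellulitis + 1 infected seroma = 2; 2/27 = 7.4% (stated as 7%).
- Two-stage minor: 2 cellulitis + 1 dehiscence = 3; 3/24 = 12.5% (as stated).
- Two-stage major: 1 expander removed; 1/24 = 4.2% (stated as 4%).

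Fisher's exact test on 2/27 against 3/24 gives p = 0.66.

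**2. Scheduled contact inside the window.** Take two months as 61 days, or 61/7 = 8.7 weeks. If biweekly means every two weeks, expansion visits fall at weeks 2, 4, 6 and 8. That is about 4 scheduled contacts in the two-stage arm and none specified in the one-stage arm. If it means twice a week, the gap is wider. The average of 5 extra visits in the cost sample is a separate figure, not confined to two months.

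**3. Contact common to both arms.** The two-week Breast Q is mailed and is not a complication check. The six-month examination is timed from completion of reconstruction. It therefore lies outside the short-term window after the first operation and comes at a different interval from that operation in each arm.

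**4. What under-detection would do.** Let d be the share of minor events detected in the one-stage arm relative to the two-stage arm. The documents give no value, so d is assumed.

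Observed one-stage rate = true one-stage rate × d. The true risk ratio that would appear as no difference = 1/d.

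| d | Observed, if true rate is 12.5% | Observed, if true rate is 20% | Risk ratio hidden (1/d) |
|---|---|---|---|
| 0.9 | 11.3% | 18% | 1.11 |
| 0.8 | 10.0% | 16% | 1.25 |
| 0.7 | 8.8% | 14% | 1.43 |
| 0.6 | 7.5% | 12% | 1.67 |

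Against a two-stage rate of 12.5%, a true excess of 20 − 12.5 = 7.5 points disappears at d = 0.6. Equal true rates of 12.5% would give the interim 7.4% at d = 7.4/12.5 = 0.59. Because d is free, that match is not evidence of bias.

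**5. Power at 72 per arm, 5% level, two-sided (sidedness assumed).** For a true 20% against 12.5%, power is 23% with equal detection. At d = 0.7 (observed 14% against 12.5%) it is about 5%, no better than the significance level.

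**The case against.** A reader might infer that the interim 7% against 12.5% shows the bias at work, or that ADM has been made to look safer than it is. The documents do not support either reading. The counts are 2 and 3, and all five minor events were treated, four with antibiotics and one with dressings. None is described as an incidental finding at an expansion visit.

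Nor should the 5 extra visits be placed inside the two-month window. They come from 10 patients at one hospital, reviewed retrospectively over November 2009 to September 2010, and they are a difference between arms. They do not show that one-stage patients go unseen. Those patients presumably have routine follow-up; the plan simply does not specify it as a complication assessment.

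Other points also stand in part:
- Expansion and the second operation may carry risks of their own, so part of any control-arm excess may be real.
- Loss of an implant or a return to the operating room would be noticed in either arm.
- Hospital accounting records clinic visits, emergency visits, surgery and stays in both arms, and could serve as a cross-check. The plan does not use it that way.
- The coordinator receives the assignment sheet and so knows the arm, but nothing shows which way that would act.
- With 23% power for 20% against 12.5%, a finding of no increase would be weak even with equal detection.

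These points limit the reach of the concern. They do not supply the missing common assessment.

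**Conclusion.** The concern holds as a risk of unequal ascertainment, of unknown size, confined mainly to short-term minor events. The documents establish that one arm has scheduled visits in the window, that the other has none specified, that no complication check is common to both, and that the planned test takes no account of this. The expected direction favours the no-increase hypothesis.

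The documents do not establish that events have been missed, or how many. The rates in the table rest on an assumed d and a 12.5% control rate taken from 3 events. The interim data are therefore neither evidence of bias nor reassurance against it. The primary Breast Q analysis is not touched. Two months from surgery is also ambiguous in Group B: if the exchange operation opens a second window, that arm has two periods at risk and the one-stage arm has one. A cheap correction is worth making while accrual continues.

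**What to change.** In iib-8 and 9c ii:

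1. Collect short-term complications in both arms with the same scripted checklist at 2 weeks (sent with the existing Breast Q mailing) and 2 months after the index operation. Ask about antibiotics, dressings, emergency visits and treatment elsewhere.
2. State which operation starts the two-month clock in Group B.
3. Record whether each event was captured by the checklist or only at an expansion visit. Compare minor events on checklist-captured events, with all recorded events as a sensitivity analysis, and report visits per arm. The checklist alone does not equalise the arms; the comparison has to rest on the common points. Some imbalance may remain, because a patient treated after an expansion visit will report that treatment.
4. Report separately the events that depend little on visit frequency: unplanned reoperation, unplanned readmission, and unplanned loss of implant or expander. The planned expander exchange must be excluded, or nearly every Group B patient would count as an event.

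The cost is a small amount of work for the existing coordinators and a change of wording. The separately reported events will be few. Ascertainment also changes mid-trial: 51 of the planned 144 (35%) were randomized at the time of writing, and those past the window cannot have the timed checklist. For them, use the hospital visit records already collected for costing, and show results before and after the change.

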### **9c. Measurement of the Primary Objective:**

#### ***i) Primary Analysis***

Each of the two domain-specific summary scores on function and satisfaction will be transformed on a scale from 0 to 100 using RUMM software. Mean scores and standard deviation for each surgery group will be calculated and compared. To address our primary aim of comparing patient satisfaction and quality of life between **Group 1** (one-stage with ADM) and **Group 2** (two-stage group without ADM) before and at the three post mastectomy follow up reference time points, we will use the **repeated measure analysis** to examine the time effect and time-group interaction. In all analyses, statistical significance will be designated at  $p <= 0.05$  level.

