### **iib-10. Sample Size**

We consider clinically relevant change in the quality of life as a difference that exceeds half a standard deviation of the baseline value. Field-testing data of the Breast Q $\odot$  has found that the standard deviation of both the psychosocial function and satisfaction distributions is approximately 20. Thus, the minimum significant difference of score in each subscale is calculated to be 10. When we set our power at 85% with a  $\beta$  error of 0.1 and a standard  $\alpha$  error rate of 0.05, and applied the equation for equal sample sizes, we calculated a **minimum sample size of 72 patients per arm** for a total sample size of 144 patients. This sample size is also sufficient with power 84%,  $\alpha$  0.05, to detect a value of 0.06 for  $\eta^2$ , representing a medium effect size of the proportion of variability in the outcome variable (Breast Q $\odot$ ) that is explained by the independent variable(s), e.g., intervention.

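### The only alternative to chi-square for complications is an undefined binomial test; in its usual one-sample form it does not compare two randomized arms, and in sparse tables it could double or triple the false-positive rate

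*Combined protocol and SAP*

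**What the plan says.** Section 9c, ii) Secondary Analysis, sets out the complication comparison in one sentence: "Group comparisons will be performed using the Pearson's chi-square test or binomial test, where appropriate for these categorical variables". No other test is named for complications, and no two-sample exact test appears anywhere in the document. The sentence gives no rule for switching, no null proportion and no reference arm.

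The comparison covers two time windows. Section iib-8 states: "Short-term complications are intra- and post-operative complications occurring within two months of surgery". Later events count as long-term.

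Section 9c, i) sets one threshold for all analyses: "statistical significance will be designated at" p ≤ 0.05. It does not say whether tests are one- or two-sided.

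The interim analysis of complication rates shows how sparse the data may be. For the two-stage arm it reports that "the rate of major complications is 4% and the rate of minor complications is 12.5" per cent. For the one-stage arm it reports no major complications and a 7% minor rate. Section iib-10 plans a "minimum sample size of 72 patients per arm".

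**The concern.** A binomial test in the ordinary sense takes one observed count and a null proportion fixed in advance. Neither arm of this trial has such a value. If the other arm's observed rate is put in its place, the test ignores the sampling error of that rate, and the true variance of the difference is about twice what the test assumes. If the reference arm has no events, the null value is zero and a single event in the other arm gives p = 0. The interim one-stage arm has no major events, so this case is not remote.

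The usual reason to leave chi-square is small expected counts, and the serious complications are the outcomes most likely to have them. Secondary objective 1 is a between-arm safety comparison. If the fallback is left undefined, the analyst picks the test and the reference arm after seeing the data, and a difference in serious complications could be declared, in either direction, more often than the nominal 5%.

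**Working it through.** **Inputs.** 72 per arm and α = 0.05 (iib-10; threshold also in 9c i). Event rates of 4%, 7% and 12.5% (interim analysis). Interim arm sizes of 17 + 10 = 27 one-stage and 16 + 8 = 24 two-stage (iia – 3). Assumptions: two-sided tests, equal true rates in the arms, one outcome per patient, 72 evaluable per arm.

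**The plan's own figure.** Section iib-10 says "the minimum significant difference of score in each subscale is calculated to be 10", with an SD of about 20 and 85% power. Then n = 2 × (1.960 + 1.036)² × 20²/10² = 2 × 8.98 × 4 = 71.8, so 72 per arm. This reproduces.

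**How often tables would be sparse.** With equal arms, the expected number of events per arm is half the total. It is below 5 when the total is 9 or fewer of 144, which corresponds to a rate under 5/72 = 6.9%. At a 4% rate, 72 × 0.04 = 2.9 events are expected per arm.

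**Large-sample check of the one-sample reading, if always used.** The test statistic has SD √2 instead of 1, so the type I error is 2 × [1 − Φ(1.96/√2)] = 2 × [1 − Φ(1.386)] = 16.6%. Exact values at 72 per arm are 15.8% (4% rate), 15.9% (7%) and 16.6% (12.5%).

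**The same reading, used only as a fallback.** All pairs of counts from two Binomial(72, p) arms were enumerated. Pearson's chi-square was used when the total was 10 or more, and the named alternative when it was 9 or fewer. The table gives the two-sided type I error.

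| True rate | Chance of 9 or fewer events | Chi-square always | Fallback: one-sample binomial | Same, zero-event reference never rejects | Fallback: Fisher | Fallback: Fisher mid-P |
|---|---|---|---|---|---|---|
| 4% | 93.6% | 4.6% | 15.2% | 10.2% | 1.4% | 2.9% |
| 7% | 44.3% | 5.2% | 10.1% | 9.6% | 4.2% | 5.0% |
| 12.5% | 1.1% | 5.0% | 5.1% | 5.1% | 5.0% | 5.0% |

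The gap between the fourth and fifth columns at 4% can be checked by hand. The chance that the reference arm has no events and the other arm has at least one is 0.96⁷² × (1 − 0.96⁷²) = 0.0529 × 0.9471 = 5.0%, and 15.2 − 5.0 = 10.2.

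**Dependence on the reference arm, 6/72 versus 2/72 (8 events, so sparse).**
- Testing 6 against 2/72: P(X ≥ 6) = 0.015. No lower-tail outcome is as unlikely as 6, since even P(X = 0) = (70/72)⁷² = 0.13. So p = 0.015.
- Testing 2 against 6/72: P(X ≤ 2) = 0.055, and with the upper tail p = 0.13.
- Fisher's exact test: p = 0.28.
- Split of 8 events against one half: 2 × (28 + 8 + 1)/256 = 0.29.

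**Interim major complications.** The reported rates imply 0/27 and 1/24. The one-sample test gives p = 0.63 with the two-stage arm as reference and p = 0 with the one-stage arm as reference. Fisher gives 0.47.

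**The case against.** The plan never says that one arm's rate is treated as known. Its sentence is about comparing groups, and the term could mean a comparison of two binomial proportions, or a conditional test of how the events split between equal arms. The second is valid: always used, its type I error is 1.0%, 1.8% and 2.0% at rates of 4%, 7% and 12.5%, against 1.0%, 2.0% and 2.9% for Fisher. Within tables of 9 or fewer events the two reject in the same cases. On that reading the plan already has a sound small-count test. The expected-count trigger is also a convention brought from outside; the plan's qualifier could refer to the type of variable.

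All of this stands, and it makes every error rate above conditional. A reader might infer that the plan raises the false-positive rate from 5% to about 16% for complications generally. The documents do not support that. The figure needs the one-sample reading and needs the test to be used whatever the counts. As a sparse-table fallback, its effect almost vanishes at 12.5%, where the fallback is reached in about 1% of trials.

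The size for very rare events also rests on how a zero-event reference arm is handled. At a 2% rate the one-sample test rejects in 21.4% of trials, but in only 3.5% if such cases are never counted as rejections.

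The objection does not supply the missing definition. The plan names a test whose ordinary meaning does not fit the comparison, and it does not state the reading that would.

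**Conclusion.** The point holds as a conditional one. The fallback for complications is undefined, and in its usual one-sample form it is the wrong kind of test for two randomized arms. If it were used in sparse tables against the other arm's observed rate, the type I error would be two to three times nominal at the interim major rate of 4% (10% to 15%), about twice nominal at 7%, and essentially nominal at 12.5%. These figures rest on an expected-count trigger and a one-sample reading that the plan does not state, as well as on two-sided testing and 72 evaluable patients per arm.

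The firmer conclusion needs neither assumption: on one set of sparse data, the readings left open give p-values from 0.015 to 0.29, so the result of a planned safety comparison depends on an unstated choice. The change is worth making. It concerns a secondary outcome only; the primary Breast Q analysis and the 72 per arm are unaffected.

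**What to change.** In section 9c ii, keep Pearson's chi-square and replace the binomial alternative and its qualifier with: *or, where any expected cell count is below 5, a two-sample exact test (Fisher's exact test, or its mid-P version), with the patient as the unit of analysis.* Choose Fisher or mid-P now, before the comparison is run.

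The cost is one clause, with no new data and no change in sample size. The downside is some conservatism at very low event counts: as the sparse-table fallback at a 4% rate, the type I error would be about 1.4% with Fisher and 2.9% with mid-P.
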